## 12.8. Deviations from the Protocol

The Investigator will not deviate from the protocol. In case of medical emergencies, the Investigator will use medical judgment and will remove the participant from immediate hazard. The Sponsor and the IEC/IRB will be notified regarding the type of emergency and course of action taken. Any permanent changes or deviations in the protocol will be validated in an amendment to the protocol.

For European studies: The amendment must be approved by the Sponsor and, if substantial as defined in directive 2001/20/EC, submitted for approval to the Health Authorities and IEC prior to being implemented. If the change implies a modification of treatment or subject evaluation tests, a new version of the informed consent form must be prepared and submitted for approval to Health Authorities and the IEC. The Sponsor will assume any responsibility or liability resulting from a change in the protocol, only if the change has been approved in writing by himself, the Health Authorities, and the IEC.

For IND studies: The amendment must be approved by the Sponsor and the IRB prior to implementation. If the change implies a modification of treatment or subject evaluation tests, a new version of the informed consent form must be prepared and submitted for approval to the IRB. The Sponsor will assume any responsibility or liability resulting from a change in the protocol, only if the change has been approved in writing by himself and the IRB.

## 12.9. Investigational Medicinal Product Drug Accountability

The Investigator must maintain accurate records of the IMP(s) received from the Sponsor. These records will include receipt and dispensing dates, and dates of return and/or destruction of unused supplies.

At trial termination, clinical supplies must be accounted for and a written clarification provided in case of discrepancies. All unused supplies must be properly destroyed at the study site or returned promptly to the Sponsor; written authorisation from the Sponsor must be obtained prior to destruction which must be documented.

When the above tasks are delegated to a Pharmacist, the Investigator remains ultimately responsible for the maintenance of accurate drug dispensing records.

## 12.10. Study Monitoring

At agreed upon times during the study and after the study has been completed, the Investigator will let Sponsor representatives periodically review the eCRF and corresponding office, hospital, and laboratory records (source documents) of each study subject. The eCRFs must be completed by the Investigator on a regular basis (within 3 working days after each subject visit) and prior to each monitoring visit.

Monitoring visits allow the Sponsor or a mandated CRO to evaluate study progress, verify accuracy and completeness of eCRFs, resolve any inconsistencies in the trial records, and ensure that all protocol requirements, applicable local laws, ICH guidelines and Investigator obligations are fulfilled..

## 12.11. Sponsor Audits

During the study or after the study has been completed, the Investigator will allow Sponsor representatives or external auditors to conduct an audit of the study. The purpose of the audit is to evaluate compliance with GCP guidelines, applicable regulations, the study protocol and the Sponsor's procedures, and to assess accuracy of the study data.

Before the audit, the Investigator will be contacted by the monitor to arrange a convenient time for the visit. Investigator and staff are expected to be present, co-operate with the auditors, and allow access to all subject records supporting the eCRFs, and other study-related documents.

## 12.12. Regulatory Agency Inspections

The Investigator may undergo a Regulatory Agency/IEC/IRB inspection during the study or after the study has been completed. The purpose of such an inspection is to conduct an official review of documents, facilities, records, and any other resources that are deemed by the authority (ies) to be related to the clinical trial.

The Investigator and staff are expected to be available for the inspection and allow access to subject records supporting the eCRFs and other study-related documents. If given advance notice of this inspection, the Investigator must contact the Sponsor immediately.

## 12.13. Disclosure of Results and Publication Policy

Results of this Phase II study will not be publicly disseminated or published until the study data are mature for the final analysis of the primary study endpoint (as defined by the protocol). The publications must be conform to the CONSORT guidelines.

However, for the purpose of submission of abstracts to congresses, a draft version of the analysis report may be generated if the Sponsor's Statistician determines prior to abstract submission that the inconsistencies remaining in the database will not affect the conclusions of the study, and that the database can be cleaned and locked in sufficient time to enable the preparation of the final statistical report by the time of presentation. In this case, the abstract should clearly stipulate that the results are not definitive.

The publication of the results of ancillary studies (e.g., translational research) is authorized at any time provided they do not mention the primary and secondary study endpoints.

All publications reporting results of this Phase II study must be reviewed and approved by the Sponsor's Statistician and Medical Monitor in charge of the study. All publications reporting results of this study must be reviewed and approved by the first author and the Study's Steering Committee. The first author is responsible for ensuring that all co-authors have seen and approved the final version of the publication prior to submission. A written agreement with the intent to submit a publication must be reached between the Sponsor, the first author and the Steering Committee.

In accordance with the International Committee of Medical Journal Editors, each author of the publication should have participated sufficiently in the work to take public responsibility for the content. All other contributors (clinicians, pathologists, ...) who do not meet sufficient criteria for authorship will be acknowledged in the publication.

For the primary publication, the first author will be the Steering Committee member who will be the primary responsible for generating the first manuscript draft, followed by the other Steering Committee members. In principle, the last author will be a Steering Committee Chairman (if different from the first author). The Investigators who enrolled evaluable subjects in the trial will be included as co-authors up to the total number of co-authors allowed by the journal, according to their contribution to subject enrollment.

Coordinators of integrated translational research components of the study or pathologists responsible for the central pathology review that is part of the study also qualify as co-authors. Two Sponsor representatives will be co-authors. These two co-authors are usually the Statistician and the Medical Monitor who were in charge of and contributed to the study.

All Investigators who enrolled evaluable subjects into the study (i.e., clinicians) or contributed scientifically to the study (i.e., pathologists, collaborators from the same institutions, ...) will be acknowledged in the publication. The acknowledgement list should include the name of all participating institutions and the name of the clinicians and other scientists involved with the study at that institution. Whenever a study participant has moved from one institution to another in the course of the study, that participant is listed with the institution to which s/he was affiliated at the time of starting his/her participation to the study, with the mention “(now at [*new affiliation*])”

Sponsor staff that made a substantial scientific contribution to the study but are not co-authors should be mentioned in the acknowledgement section (i.e., data managers, clinical scientists, clinical trial managers).

The person who took the lead in conducting an ancillary study is the first author of the relevant publication. The Sponsor representatives who contributed to the analysis and publication, if any, will also be co-authors. The list of co-authors must be approved by the Study's Steering Committee and Sponsor.

## **12.14. Insurance Policy**

The Sponsor will subscribe a liability insurance covering his and the Investigator's responsibility as well as the responsibility of any person involved in the conduct of the study, provided there is proper adherence to the protocol. An insurance certificate will be provided by the Sponsor to the IEC/IRB if required.

## **12.15. Premature Study Discontinuation**

The trial may be prematurely terminated by the Sponsor, the Investigator or the IEC/IRB at any time. If the study is prematurely terminated, the Investigator must promptly inform the study subjects and ensure that they receive appropriate therapy and follow-up. All procedures and requirements pertaining to study closure as defined by the Sponsor will be carried out.

If the Investigator terminates the trial, s/he should promptly inform the Sponsor and the IEC/IRB and provide a detailed written explanation of the termination. If the Sponsor terminates the trial, the Investigator should promptly inform the IEC/IRB and provide a detailed written explanation of the termination. If the

IEC/IRB terminates the trial or suspends its approval, the Investigator should promptly inform the Sponsor and provide a detailed written explanation of the termination.

## 14. APPENDICES

Appendix A	ECOG Performance Status
Appendix B	RECIST criteria
Appendix C	NCI-CTCAE v5.0 criteria
Appendix D	World Medical Association Declaration of Helsinki
Appendix E	Hyperphosphatemia management guidelines
Appendix F	Dermatological toxicity prophylaxis and management guidelines
Appendix G	Hypercalcemia treatment guidelines

**Appendix A: ECOG Performance Status**

ECOG PERFORMANCE STATUS*	
Grade	ECOG
0	Fully active, able to carry on all pre-disease performance without restriction
1	Restricted in physically strenuous activity but ambulatory and able to carry out work of a light or sedentary nature, e.g., light house work, office work
2	Ambulatory and capable of all self-care but unable to carry out any work activities. Up and about more than 50% of waking hours
3	Capable of only limited self-care, confined to bed or chair more than 50% of waking hours
4	Completely disabled. Cannot carry on any self-care. Totally confined to bed or chair
5	Dead

\* As published in Am. J. Clin. Oncol.:

**Appendix B: RECIST Criteria**

Please refer to RECIST guidelines version 1.1 (Eur J cancer. 2009; 45(2):228-247) by using the link below:

<http://recist.eortc.org/wp-content/uploads/2015/03/RECISTGuidelines.pdf>

**Appendix C: NCI-CTCAE v5.0 criteria**

The NCI-CTCAE v5.0 criteria can be consulted at:

[https://ctep.cancer.gov/protocolDevelopment/electronic\\_applications/docs/CTCAE\\_v5\\_Quick\\_Reference\\_8.5x11.pdf](https://ctep.cancer.gov/protocolDevelopment/electronic_applications/docs/CTCAE_v5_Quick_Reference_8.5x11.pdf)

**Appendix D: World Medical Association Declaration of Helsinki**

The declaration of Helsinki can be consulted at:

<https://www.wma.net/wp-content/uploads/2016/11/DoH-Oct2013-JAMA.pdf>

## Appendix E: Hyperphosphatemia management

These are suggested guidelines based on emerging data from studies testing FGFR inhibitors and from experience of participating Investigators and certified pharmacists. However, clinical judgment by the treating physicians and local SOC must be followed to decide which management is the best for each case of hyperphosphatemia.

### A. Initial Treatment

Serum phosphorus levels	Intervention
5.5 – 6.9 mg/dL	
Continue treatment with Debio 1347 at current dose AND start on sevelamer oral POWDER 1200mg three times a day (subjects may use tablets if preferred, but tends to have more gastrointestinal toxicity) AND
 
Escalate to sevelamer oral POWDER or tablets 2400mg three times a day if tolerated.
 <hr/> 
Reassess serum phosphorus within 7 days

≥ 7 mg/dL	
Hold treatment with Debio1347
 
Start sevelamer oral POWDER or tablets 2400mg three times a day
 <hr/> 
Add treatment with lanthanum carbonate (Fosrenol®) 1g three times a day
 <hr/> 
Reassess serum phosphorus level within 7 days: If serum phosphorus level < 5.5 mg/dL → resume Debio 1347 at same dose and recheck within 7 days of resumption

	
N.B.
 
 
- Sevelamer should be preferably taken in the mid of meals
 
- Lanthanum carbonate should be taken just after meals
 
- Sevelamer and lanthanum must be administered at least 2 hours after or 4 hours before Debio 1347
 

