## 5.2. Study Treatment

Subjects will receive Debio 1347 tablets at the dose of 80 mg once daily from Day 1 to Day 28 in 28-day cycles until occurrence of any of the criteria described in Section 8.4.1.

Debio 1347 method of administration is described in Section 7.6.

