## 5.3. Dose Modifications

### 5.3.1. Debio 1347 dose adjustment

Individual dose adjustment of Debio 1347 may be considered and applied as per Table 5-1 below if required. Non-treatment related or unexpected toxicities may also require treatment interruption at the discretion of the Investigator and Medical Monitor. For guidance on toxicity management, please refer to appendices E, F, and G.

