**Table 5-1 Debio 1347 dose adjustment**

ADVERSE EVENT	GRADE	ACTION
Febrile neutropenia, Neutropenia with infection	4	Permanent discontinuation
	3	Temporary discontinuation until recovery to ≤ Grade 1
Neutropenia	3, 4	Temporary discontinuation until recovery to ≤ Grade 2
Thrombocytopenia	4	Temporary discontinuation until recovery to ≤ Grade 1
	3	If a platelet transfusion is required, temporary discontinuation until recovery to ≤ Grade 1
Diarrhea, constipation, nausea, vomiting, alopecia or skin toxicity	3, 4	Temporary discontinuation until recovery to ≤ Grade 1, but Grade 2 diarrhea manageable with drugs can restart the treatment at 60 mg QD
Hypertension	4	Permanent discontinuation
	3	If uncontrolled, temporary discontinuation until recovery to ≤ Grade 2
Hepatotoxicity (e.g., AST, ALT, ALP increased)	4	Permanent discontinuation
	3	Temporary discontinuation until recovery to ≤ Grade 2
Other non-hematological toxicity (except for alopecia and clinically insignificant electrolyte abnormalities)	4	Permanent discontinuation
	3	Temporary discontinuation until recovery to ≤ Grade 1 or baseline
Hyperphosphatemia		Please refer to treatment guidelines in Appendix E
Recovery from the above AEs		Permanent discontinuation if failure to recover within 21 days, otherwise retreatment at 60 mg QD
Dermatologic toxicities		Please refer to treatment guidelines in Appendix F
Hypercalcemia		Please refer to treatment guidelines in Appendix G

Abbreviations: ALP, alkaline phosphatase; ALT, alanine aminotransferase; AST, aspartate aminotransferase; QD, once daily

In the event a subject requires temporary treatment discontinuation, the Investigator may choose to increase the frequency of the assessments until resolution.

Subjects will be permanently discontinued if a second reduction is necessary. Reduced doses may not be re-escalated. Nevertheless, if according to the Investigator a further increase of the dose to 80 mg daily is expected to improve the clinical benefit of a subject, this increase may be considered after discussion between the Investigator and the Medical Monitor of the study.

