**XEROSIS (DRY SKIN)**

Severity (CTCA v.4.03)	Intervention

Grade 0
	
Prophylaxis with urea 10-20% moisturizing cream twice daily Fragrance-free detergents and soaps

Grade 1 Covering < 10% BSA and no associated erythema or pruritus or Grade 2 Covering 10-30% BSA and associated with erythema or pruritus; limiting instrumental ADL
	
Continue treatment of Debio 1347 at current dose and monitor for change in severity
 <hr/> 
Continue moisturizer with urea 10-20% cream and consider adding a mid-potency topical steroid cream (i.e. Triamcinolone 0.1% cream or a steroid cream with equivalent potency)
 <hr/> 
Reassess after 2 weeks (either by healthcare professional or subject self-report); if reactions worsen proceed to next step

Grade 3 Covering > 30% BSA and associated with pruritus; limiting self-care ADL
	
Interrupt treatment of Debio 1347 until severity decreases to grades 0-1
 <hr/> 
Consider treatment with topical steroid cream twice a daily (e.g. Triamcinolone 0.1% cream or a steroid cream with equivalent potency)
 <hr/> 
Reassess after 2 weeks:
 
 
1. If reactions worsen or do not improve, dose reduction per Principal Investigator clinical judgment may be necessary
 
2. Treatment discontinuation should be reserved after dose reduction.
 

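### Table 5-1 and Appendix F give different restart and stopping rules for Grade 3 skin toxicity, and Table 5-1, read by row order, differs from Appendix E on the first hyperphosphatemia restart

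*Protocol*

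**What the plan says.** **Starting dose and status of the texts.** Section 5.2: "Subjects will receive Debio 1347 tablets at the dose of 80 mg once daily from Day 1 to Day 28". Section 5.3.1 says that dose adjustment "may be considered and applied as per Table 5-1 below if required" and adds "For guidance on toxicity management, please refer to appendices E, F, and G". Appendices E and F each describe themselves as suggestions that yield to clinical judgment and local standard of care. No sentence ranks Table 5-1 against the appendices.

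**Table 5-1.** One row covers "Diarrhea, constipation, nausea, vomiting, alopecia or skin toxicity" at Grades 3 and 4 and interrupts treatment until recovery to Grade 1 or lower. Further down, the hyperphosphatemia row gives no grade and no action, only "Please refer to treatment guidelines in Appendix E". Below both comes "Recovery from the above AEs": permanent discontinuation without recovery in 21 days, otherwise retreatment at 60 mg once daily. Only after that row do dermatologic toxicities and hypercalcemia appear, referred to Appendices F and G. Text under the table stops treatment permanently if a second reduction is needed. It bars re-escalation, but allows a return to 80 mg to be considered after discussion with the Medical Monitor.

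**Appendix F (Grade 3 paronychia, hand-foot syndrome, xerosis, oral mucositis).** Treatment is interrupted and the event reassessed after 2 weeks. Then: "If reactions worsen or do not improve, dose reduction per Principal Investigator clinical judgment may be necessary". Discontinuation is kept for after a dose reduction. No restart dose is stated.

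**Appendix E.** Section 7.7.2.5 also sends hyperphosphatemia here. Under part A (initial treatment), phosphorus of 7 mg/dL or more leads to a hold and, once the level is below 5.5 mg/dL, to "resume Debio 1347 at same dose and recheck within 7 days of resumption". Under parts B and C (second and subsequent modifications), a hold at 7 mg/dL or more ends with resumption at a reduced dose.

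**The concern.** The same Grade 3 skin event falls under two rows of one table, and the two rows lead to different instructions on both restart and stopping. Hyperphosphatemia has a related but weaker problem: its row defers to Appendix E, yet it stands above a recovery row that claims everything over it, while the other two referrals were placed below that row.

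Two sites could therefore handle the same event differently and each point to the protocol. What is at stake is the dose received after the event and whether the single permitted reduction has been used up. In some courses it is also whether the subject stays on treatment. Hyperphosphatemia is not a rare trigger: Section 3.3.2 lists it among the Phase I events with incidence above 25% and among those most often above Grade 2. Section 9.1.3 equates 7 to 9.9 mg/dL with about Grade 3, and part A's hold begins at 7 mg/dL.

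**Working it through.** The plan gives no statistical figure to reproduce here. The check is a side-by-side reading plus dose arithmetic.

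**Skin toxicity, Grade 3** (Appendix F has no Grade 4 entry, so the comparison stops there).

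| Course | Table 5-1, skin row plus recovery row | Appendix F |
|---|---|---|
| Recovers to Grade 1 or lower within 21 days | Restart at 60 mg once daily | No restart dose; reduction is raised only if the reaction worsens or fails to improve |
| Not recovered within 21 days | Permanent discontinuation | Reduction may be considered at the 2-week reassessment; discontinuation only after reduction |

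The two texts agree on the recovery grade (0–1) for hand-foot syndrome, xerosis and mucositis. They differ on what follows. Oral mucositis may not count as skin toxicity, but it would then fall under the other non-hematological row, which at Grade 3 also stands above the recovery row.

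**Hyperphosphatemia, subject on 80 mg, first managed under part A at 7 mg/dL or more, then below 5.5 mg/dL** (and within 21 days, so that the recovery row's restart clause is the one in play).

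- Recovery row applied by position: 60 mg, that is 3 × 20 mg tablets.
- Appendix E part A: same dose, 80 mg, that is 4 × 20 mg tablets.
- Difference: 80 − 60 = 20 mg/day; 20/80 = 25%.

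**What follows if phosphorus again reaches 7 mg/dL and part B applies.**

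| First restart | Reduction under part B is | Consequence under the text below Table 5-1 |
|---|---|---|
| 60 mg (recovery row) | the second | Permanent discontinuation |
| 80 mg (Appendix E part A) | the first | Treatment continues at a reduced dose |

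Parts B and C resume with a reduction, so they do not conflict with the recovery row on restart dose. Appendix E sets no 21-day limit, but that is silence: the limit could apply alongside it.

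**Effect on the analysis.** SAP Section 10.3.1 counts dose reductions, computes dose intensity, and uses 60 mg instead of 80 mg as the planned daily dose in reduced periods. The first two depend on which rule a site followed. On days fully dosed after a 60 mg restart, compliance is 60/60 = 100%. Even against an 80 mg plan those days give 60/80 = 75%, which is not below the 75% limit used for the PP population in SAP Section 7.4.

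**The case against.** The strongest reply concerns hyperphosphatemia. Its row in Table 5-1 carries no grade, recovery criterion or action of its own, whereas the recovery row presupposes a criterion. Appendix E supplies one (below 5.5 mg/dL), and Section 7.7.2.5 directs treatment there as well. Full deferral to Appendix E is thus a natural reading, and the contrary reading rests on row order alone. Section 5.3.1 is also worded permissively. This stands in part: the hyperphosphatemia conflict is the weaker of the two. It is not removed, because no sentence exempts that row from the one below it. The reply does not reach skin toxicity, which has its own criterion and action above the recovery row and a competing referral beneath it.

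A reader might also infer more than the documents support:

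- *That Appendix F restarts at the same dose.* It states no restart dose.
- *That every first interruption at 7 mg/dL or more is affected.* A subject first managed at 5.5–6.9 mg/dL who later reaches 7 can fall under part B, which itself reduces. A subject already on 60 mg restarts at 60 mg on either reading.
- *That the 20 mg gap lasts for the rest of treatment.* A later part B or C reduction can close it, and a return to 80 mg may be considered with the Medical Monitor.
- *That the Phase I incidence above 25% measures how often this happens.* That figure is any-grade, across 10 to 150 mg. The rate of first presentation at 7 mg/dL or more on 80 mg is not given.

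Finally, enrolment is halted and SAP Section 9.3 says the study ended earlier than expected, so little dosing may remain to be changed. That limits the benefit of an amendment, but not the need to report what was done.

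**Conclusion.** The inconsistency is real, and clearest for Grade 3 skin toxicity. A fixed 60 mg restart with a 21-day stopping rule stands against a conditional, discretionary reduction with discontinuation only afterwards, and nothing says which governs. For hyperphosphatemia it holds only if the recovery row is taken to cover the row above it, and only at a restart after a first hold under Appendix E part A in a subject on 80 mg.

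In that case the difference is 20 mg/day (25%) at restart, and a later part B reduction becomes either the first or the disqualifying second. For skin toxicity the gap cannot be fixed, because Appendix F names no dose; it would also be 20 mg/day if a site restarted at 80 mg. The number of subjects affected cannot be derived from the documents.

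The effect on the analysis is confined to exposure summaries. The ORR test and sample size are untouched. A reader might infer that site reading changes PP membership, but no direct effect is shown: the planned dose falls with the reduction, and PP is only supportive to the ITT analysis. No view is taken here on which dose or stopping rule is right.

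**What to change.** Reconcile Table 5-1, Section 7.7.2.5, Appendix E parts A to C and Appendix F so that each toxicity has one restart rule and one discontinuation rule. State expressly whether the recovery row, including its 21-day limit, covers hyperphosphatemia and skin toxicity, and which text governs when the table and an appendix differ. If dosing has already ended, state in the clinical study report which rule was applied, so that the counts of dose reductions and the dose intensity can be interpreted.

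The cost is a protocol clarification, or a short statement in the report. No new data are needed.
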